5.7.2 Clinical laboratory

Haematology	Chemistry	Urinalysis
Hemoglobin	Sodium	Leukocytes
Erythrocytes	LDH(Lactate dehydrogenase)	Nitrite
Hematocrit	Potassium	Urobilinogen
Thrombocytes	Creatinine	Protein
Leukocytes	Serum bilirubin level	pH
	AST (Aspartate aminotransferase)	Occult blood (erythrocytes,
		leucocytes)
	ALT (Alanine aminotransferase)	Specific gravity
	Urea	Ketones
	ALP (Alkaline phosphatase)	Bilirubin
	FSH (Follicle-stimulating hormone)	Glucose
	(for postmenopausal women only)	

The following laboratory safety data are collected for this study:

Laboratory safety data for haematology, biochemistry and urinalysis will be summarized using descriptive statistics and listed per visit, using protocol visits. Change from baseline will be calculated and presented as well for quantitative data, using the same summary statistics. If applicable, laboratory safety data collected as additional/unscheduled assessments (i.e. apart from those per protocol) will only be listed and will not be used in summary statistics. Baseline is defined as the Visit 2 measurement. In case the Visit 2 measurement is missing, the Visit 1 measurement will be used.

For laboratory safety data, all recorded and determined laboratory safety data will be listed, including information on the reference ranges, if available. In addition, information regarding age at screening and sex will be added to the listing.

All safety laboratory parameters will be presented in the tables and listings in the same standard units as supplied, which will be SI units.

Lastly, for clinical laboratory parameters, a listing will be created presenting all data that are out of reference range on a per-patient level, including any available unscheduled measurements. Note that clinical significance for out-of-range values is not collected per eCRF and can therefore not be presented. Information regarding age at screening and sex will be added to this listing. The SAF population is used for the presentations.

5.7.3 Vital Signs

Vital sign data consist of measurements for pulse rate and systolic/diastolic blood pressure (sitting). Vital signs will be summarized and listed per visit (protocol visits). Change from baseline will be calculated and presented as well, using the same summary statistics. Visit 2 is considered the baseline visit for vital signs; in case Visit 2 is missing, the Visit 1 measurement will be used as baseline instead. If applicable, vital sign measurements collected as additional/unscheduled assessments (i.e. apart from those per protocol) will only be listed and will not be used in summary statistics. The SAF population is used for the presentations.

Clinical Study Reference: IB1001-202

5.7.4 Electrocardiography (ECG)

ECG outcome results (corrected QT interval and normal/abnormal result) will be presented descriptively per protocol visit. If applicable, ECG measurements collected as additional/unscheduled assessments (i.e. apart from those per protocol) will only be listed and will not be used in summary statistics. The SAF population is used for the presentations.

5.7.5 Prior and concomitant medication/therapies

The use of prior and concomitant medication/therapies will be listed for all subjects: included will be the preferred term, World Health Organization (WHO) coding information and the Anatomic Therapeutic Chemical (ATC) class code), dose, route of administration, start and stop date, frequency and reason for administration, as well as information if given for an AE. Differentiation will be made between prior and concomitant medication/therapies, by creating two separate listings. A frequency table per ATC class code and WHO drug code will be created if considered relevant, separately for prior and concomitant medication/therapies. The SAF population is used for the presentation.

5.8 Scheduled visits, dosing, and treatment compliance

5.8.1 Visit dates

A listing with actual visit dates (and times, if applicable) per patient will be presented.

5.8.2 Dosing and treatment compliance

Relevant dosing information (first dosing date, last dosing date), scheduled and actual dosing dates/times and treatment compliance information will be determined and listed for each patient. Summary statistics for the number of N-Acetyl-L-Leucine doses taken, based on bottles of dispensed and returned unused bottle counts, will be calculated for Visit 3 and Visit 4 if this information is collected on a per-visit basis. Compliance is defined as 100% * (total number of IB1001 bottles and/or sachets dispensed – total number of IB1001 unused bottles and/or sachets returned), divided by the number of bottles and/or sachets which should have been used. Note that the number of bottles the patients should have used depends on the dosage they should take (see Section 2.3 for reference) and the duration of the treatment period. Considering the fact that the patient's total daily dose may be reduced by up to half of their assigned dose at the discretion of the investigator, the actual dose will be used to determine the correct compliance calculation, if collected in the eCRF. The proportion of patients who take at least 80% of the prescribed medication will also be shown. Total dosing period is defined as the duration (in days) between first dose date and last dose date.

6 EXTENSION PHASE: STATISTICAL ANALYSIS

6.1 General considerations

The Extension phase is considered the study period starting with the Extension phase baseline (Visit 7) until Visit 12. In principle, data presentations will be created for the full Extension phase. Only where applicable and relevant, a separation will be made as follows:

- Extension phase I: Extension phase Visit 7 until Visit 10.
- Extension phase II: Extension phase Visit 10 until Visit 12.

Clinical Study Reference: IB1001-202

All evaluations will be exploratory in nature, and all endpoints for the complete Extension phase are considered secondary to the endpoints of the Parent study. Statistical analysis will only be applied for some of the endpoints as defined for Extension phase I, no statistical analyses will be done for the endpoints in Extension phase II.

Summary presentations and listings will be presented and only reported data will be presented (i.e. no imputation or LOCF will be done) for data collected during Extension phase II. If not otherwise defined, data will we presented as missing where applicable.

Raw data (in listings) will be presented in the same precision as received. Appropriate rounding will be performed for the following summary statistics, where applicable: mean, standard deviation (SD) and two-sided 90% confidence limits will be presented with at least one more decimal than the original data; minimum and maximum values will be presented with the same precision as the original data. In frequency tables, percentages will be presented with 1 decimal unless otherwise stated.

P-values will be presented with 3 decimals, and those smaller than 0.001 will be replaced by <0.001. One-sided p-values smaller than 0.05 will be considered statistically significant for the primary endpoint and indicative for other endpoints. No adjustment for multiple comparisons will be applied. Conclusions regarding treatment efficacy will not solely rely on detecting statistical significance but equal emphasis will be placed on the magnitude and clinical relevance of treatment differences as judged by the point estimates.

Descriptive statistics presented in general summary tables will be the number of non-missing observations (n), mean, SD, minimum, median and maximum for quantitative data. For categorical data, frequency counts and percentages will be determined.

For the full Extension phase, the measurement at Visit 7 is considered the baseline. In case of missing Visit 7A data for safety measurements (e.g. for safety lab), and Visit 7B has occurred within 1 (+6) days of Visit 6, the Visit 6 data from the Parent study should be used instead (data are not being re-entered in the database): see also Section 2.2.2 for clarification.

No screen failures will be present in the data.

For the full Extension phase, a treatment emergent adverse event (TEAE) is defined as an adverse event that appears during or after the start of study treatment in the Extension phase at Visit 7B and was absent before. As a consequence, adverse events occurring during the washout phase between V9 and V10 will also be considered treatment emergent.

6.2 Adjudication of endpoint data

Videos of the primary and non-primary anchor tests are collected throughout the extension phase for the CI-CS. These videos may be analyzed in order to inform the development and validation of the CI-CS but will not be reported in the CSR (and hence not listed or tabulated). Data received will be included as-is in the CDISC files. In case of analysis, the following process applies: For the CI-CS assessments of both the primary and non-primary anchor tests, after a patient completes Visit 10 of the Extension phase, the independent raters will be given 3 video pairs of from Visit 7 to Visit 9, Visit 9 to Visit 10, and Visit 7 to Visit 10. After a patient completes Visit 12 of the Extension phase, the independent raters will be given a video pair from Visit 10 to Visit 12 (the raters may also assess additional video pairs, i.e. Visit 1 to Visit 12, on an exploratory basis). After a patient completes Visit 12 of the Extension phase, the independent

Clinical Study Reference: IB1001-202

raters will be given a video pair from Visit 10 to Visit 12 (the raters may also assess additional video pairs, i.e. Visit 1 to Visit 12, on an exploratory basis). The videos will be presented in a random order, and the independent raters will be blinded to the timepoint corresponding to each video. The appropriate Likert scale score will be provided to each of the videos and pairs of videos. For further details regarding scoring and adjudication, which will be similar to that of the Parent study, see Section 5.2.

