2.3 Exploratory Objectives

The exploratory objectives are:

- To assess the clinical efficacy of long-term treatment with N-Acetyl-L-Leucine on symptoms, functioning, and quality of life for patients with GM2 Gangliosidosis
- To assess the effects of a 42-day (+14 days) washout from N-Acetyl-L-Leucine after oneyear treatment on symptoms, functioning, and quality of life for patients with GM2 Gangliosidosis

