2.1.2 Extension phase

Primary Objective

The primary objective in the Extension Phase is to evaluate the efficacy of N-Acetyl-L-Leucine based on the Modified Disability Rating Scale (mDRS).

Secondary Objectives

The secondary objectives are:

Clinical Study Reference: IB1001-202

- To evaluate the long-term safety and tolerability of N-Acetyl-L-Leucine at 4 g/day in patients aged ≥13 years, and weight-tiered doses in patients 6 to 12 years of age, with GM2 Gangliosidosis
- To characterize the pharmacokinetics (PK) of N-Acetyl-L-Leucine in patients with GM2 Gangliosidosis.

Exploratory Objectives

The exploratory objectives are:

- To assess the clinical efficacy of long-term treatment with N-Acetyl-L-Leucine on symptoms, functioning, and quality of life for patients with GM2 Gangliosidosis
- To evaluate the effects of a 42-day (+14 days) washout from N-Acetyl-L-Leucine after one-year treatment based on blinded raters' Clinical Impression of Change in Severity (CI-CS)
- To assess the effects of a 42-day (+14 days) washout from N-Acetyl-L-Leucine after one-year treatment on symptoms, functioning, and quality of life for patients with GM2 Gangliosidosis.
- To evaluate the long-term clinical efficacy, safety and tolerability of N-Acetyl-Lleucine for patients with GM2 Gangliosidosis

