4.2.3 Exploratory Endpoints

Exploratory endpoints will investigate other measures of symptoms and quality of life from Visit 7 to Visit 9 for the following measures:

Measurement of Ataxia and Functioning

- Spinocerebellar Ataxia Functional Index (SCAFI). The SCAFI is composed of the 8MWT, the 9HPT, and the PATA rate, a measure of speech performance.
- Scale for Assessment and Rating of Ataxia (SARA) score. SARA has 8 items that are related to gait, stance, sitting, speech, finger-chase test, nose-finger test, fast alternating movements and heel-shin test.

Measurement of Health-related Quality of Life

• Quality of Life EQ-5D-5L for patients aged ≥18; EQ-5D-Y for children aged 6-17 years (two parts: the EQ visual analogue scale (EQ-VAS) and the EQ descriptive system).

Clinical Study Reference: IB1001-202

Measurement of Global Impression

- Clinical Global Impression of Severity by the treating physician (CGI-S-physician).
- Clinical Global Impression of Change by the treating physician (CGI-C-physician).
- Clinical Global Impression of Severity by the caregiver (CGI-S-caregiver).
- Clinical Global Impression of Change by the caregiver (CGI-C-caregiver).
- Clinical Global Impression of Severity by the patient (CGI-S-patient) if they are able.
- Clinical Global Impression of Change by the patient (CGI-C-patient) *if they are able.*

The CGI-S scales are on a 7-point scale ranging from 'normal, not ill at all' to 'among the most ill patients'. The CGI-C scales are also on a 7-point scale ranging from 'very much improved' to 'very much worse'.

Videos of the primary and non-primary anchor tests are collected throughout the extension phase for the CI-CS. These videos may be analyzed in order to inform the development and validation of the CI-CS.

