12.3 End-of-text tables and graphs

Following ICH E3 guidelines, all tables and graphs mentioned here will be presented in Section 14 of the CSR, and tables will be prepared in the order and with section number as stated.

Table/graph number	Contents of table/graph

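### The SAP sets a blinded CI-CS objective for the one-year washout and lists CI-CS output for the study report, but Section 6.2 says the ratings will not be reported

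*SAP*

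**What the plan says.** **Objective.** SAP 2.1.2 lists, under the Extension's exploratory objectives, an evaluation of the "washout from N-Acetyl-L-Leucine after one-year treatment based on blinded raters' Clinical Impression of Change in Severity (CI-CS". The matching objective in Protocol Appendix 6, Section 2.3, concerns the effects of a "washout from N-Acetyl-L-Leucine after oneyear treatment on symptoms, functioning, and quality of life" and does not name CI-CS.

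**Reading and reporting.** SAP 4.2.3 says "These videos may be analyzed in order to inform the development and validation of the CI-CS". SAP 6.2 repeats this, then adds "but will not be reported in the CSR (and hence not listed or tabulated". If the videos are read, "the independent raters will be given 3 video pairs of from Visit 7 to Visit 9, Visit 9 to Visit 10", plus Visit 7 to 10, in random order and blind to timepoint. On storage, "Data received will be included as-is in the CDISC files".

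**Analysis sections.** SAP 4.2.4 lists the measures that may be compared between Visits 9 and 10, and CI-CS is not among them. SAP 6.6.3 and 6.6.4 describe no CI-CS summary.

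**Output lists.** SAP 12.3 says "all tables and graphs mentioned here will be presented in Section 14 of the CSR", and its Extension list opens with CI-CS tables 14.2.63 to 14.2.70. SAP 12.4 sends listing 16.2.5.9, individual CI-CS scores, to CSR Section 16.2.

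**Protocol Appendix 6.** Section 5.5 states that the videos and pairs will be assessed blind. Sections 6.1.2, 8.5.2 and 8.7 say only that they may be analysed.

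**The concern.** An objective should lead to a named analysis and a place in the report. Here the objective names its instrument, the analysis sections omit that instrument, one section bars its results from the report and two others list them for it. Two programmers could each follow this SAP and deliver different reports.

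The stake is blinding. The Extension is open-label. SARA and SCAFI are scored by the investigator or site team, mDRS by an investigator, CGI by physician, caregiver or patient, and EQ-5D by the patient. All of them can know that drug stopped at Visit 9. CI-CS is the only measure of that withdrawal scored by people who do not know the timepoint, and it has the same form as the withdrawal half of the parent primary endpoint. With an optional read and a reporting bar, a blinded result could be obtained and left out while open-label changes over the same interval are tabulated. This describes what the wording permits. It alleges no intent.

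**Working it through.** No sample size, power or significance calculation bears on this point. The check is to follow the SAP's instructions through each case.

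**1. Are the data there?** Yes. The Extension schedule of events has anchor-test videos at Visits 7, 9 and 10, and SAP 6.2 with 5.2 already describes pairing, random order, blinding and adjudication. SAP 2.4.2 expects 20 of 32 patients to roll over, so there would be up to 20 Visit 9 to 10 pairs on the primary anchor if every video is readable.

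**2. What happens under each instruction?**

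| Case | SAP 6.2 | SAP 12.1, 12.3, 12.4 | Objective in 2.1.2 |
|---|---|---|---|
| Videos not read | No CI-CS output | Tables and listing produced empty, marked as having no data | Unanswered |
| Videos read, 6.2 followed | Ratings kept in the CDISC files, absent from the CSR | Instruction broken | Unanswered in the report |
| Videos read, 12.3 and 12.4 followed | Instruction broken | Eight tables and one listing in the CSR | Answered only if Visit 9 to 10 is among the changes shown |

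No case satisfies 2.1.2, 6.2 and 12.3/12.4 together.

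**3. Would the listed tables answer the objective?** Not reliably. Table 14.2.64 promises changes between visits without naming the pairs. Tables 14.2.63, 14.2.65 and 14.2.66 call CI-CS the Extension primary endpoint, and 14.2.63 carries a p-value on a CI-CS success rate. SAP 4.2.1 and 6.6.1 make the primary endpoint success on mDRS. No success rule for CI-CS is defined, and the list has no table for the mDRS success test: 14.2.78 and 14.2.79 are descriptive only.

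**4. Is there a recorded reason?** No. SAP Section 7 notes other departures, such as dropping the ASIS analysis. It mentions neither the added CI-CS objective nor the reporting bar.

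**5. Which pair answers the objective?** Visit 9 to 10 spans 42 days (+14), close to the parent washout of 42 days (+7). Visit 7 to 9 spans 365 days (±14), whereas parent raters are asked about change over six weeks. Protocol Appendix 6, Section 8.5.1, postulates that 90% of patients under standard of care worsen on mDRS over 12 months. Visit 7 to 9 therefore mixes a year of expected progression with any drug effect.

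**The case against.** The best defence is that SAP 6.2 is the section that follows the protocol. The protocol's washout objective does not name CI-CS, and three of its four statements on the Extension videos leave the reading optional, for developing and validating the scale. On that view the stray item is the objective in SAP 2.1.2, the tables in 12.3 are leftovers, and deleting both resolves the conflict as well as reporting would. This stands: deletion is a legitimate route, and nothing in the protocol obliges the sponsor to read the videos. It does not rescue the current text, because the objective and outputs have not been deleted.

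It is also fair that the bar applies to favourable and unfavourable ratings alike, that ratings received are retained, that SAP 6.1 calls all Extension evaluations exploratory, and that Section 7 rests trial success on the parent primary endpoint alone.

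A reader might infer three stronger things that the documents do not support:

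- *That the blinded Extension ratings are simply kept out of the report.* SAP 12.3 and 12.4 still list them for it, so their fate is unresolved.
- *That Visit 7 to 9 minus Visit 9 to 10 would replicate the parent endpoint.* It would subtract a six-week change from a one-year change.
- *That the parent planning SD of 1.02 and mean of 0.45 give the precision of an Extension comparison.* They are design assumptions for a difference of two six-week changes, and no document gives a variance for either Extension interval.

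**Conclusion.** The SAP is wrong as written on this point. It sets an objective, withholds the analysis, and gives opposite instructions on reporting. The consequence is limited: one exploratory objective and up to about 20 patients' blinded withdrawal ratings, with no effect on the parent primary analysis or on the Extension's mDRS test. What makes it worth correcting is that these are the only rater-blinded data on stopping after one year, and the text lets them be read and left out.

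The conclusion rests on the wording alone. The figure of 20 is the SAP's own rollover expectation and assumes readable videos at Visits 9 and 10. Because the reading is optional, the finding supports reporting whatever is read. It does not support requiring the read.

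**What to change.** **If any Extension video may be read.** Delete the reporting bar in SAP 6.2 and put in its place:

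> *Every Extension CI-CS pair that is read will be listed and summarised descriptively in the mITTe in the CSR, whatever the result. Visit 9 to Visit 10 on the primary anchor (n, mean, SD, two-sided 90% CI, frequency table) supports the exploratory objective in Section 2.1.2. Visit 7 to Visit 9 will be shown separately as a one-year change. The difference between the two will not be presented as a replicate of the parent endpoint.*

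Then align the rest:

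- Add CI-CS to SAP 4.2.3, 4.2.4, 6.6.3 and 6.6.4 in the same terms.
- In 12.3, name the visit pairs in the CI-CS tables, and correct 14.2.63, 14.2.65 and 14.2.66 so that the primary-endpoint tables refer to mDRS. Keep listing 16.2.5.9 in 12.4.
- Record the change in Section 7, and state there which of the two protocol statements on reading the videos is being followed.

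**If the sponsor will not read the videos.** Delete the CI-CS objective from 2.1.2 and the CI-CS items from 12.3 and 12.4, and say so in Section 7, before any Extension rating is seen.

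**Cost.** SAP wording, plus descriptive tables most of which 12.3 already lists. The real price is that the sponsor commits to reporting any exploratory reads that are done, favourable or not.

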6.3 Missing data

Data from withdrawal patients will be included in the analysis until their last assessment.

For handling missing data in Extension phase, similar approaches as described in Section 5.3 will be followed, with the alteration that "first dose date" is the first dosing during Extension phase I or II, respectively. For AE and concomitant medication this indicates that events started during the Parent study and continuing during Extension phase will be considered prior for the Extension phase.

6.4 Interim analysis

Per patient data listings and summary tables/plots will be provided for several DSMB meetings as specified in the DSMB Charter created for the Parent study.

The final CSR will be written upon the completion of the full Extension phase, and no interim analysis is performed during the Extension phase.

6.5 **Baseline characteristics**

6.5.1 Inclusion/exclusion criteria

An individual patient listing of the deviations from inclusion criteria will be presented. No exclusion criteria are collected for the Extension phase, and no separate inclusion is done for Extension phase II.

6.5.2 Demographics

Demographic data at baseline will be summarized for all patients and by the 4 age/weight/dosing groups (using Visit 7 information) in tabulations, even if there is a change in dose between Visit 7 and 8, or between Visit 8 and 10, or Visit 10 and 11 (see Section 2.3.2).

Appropriate descriptive statistics for age, height, weight, BMI, ethnic group and sex will be given. The summary will be created for each analysis population separately. Additionally, demographic data will be listed.

